9.1.2. Exclusion criteria

Exclusion criteria for part 1 and 2

Patients meeting the following criteria will not be included in the study:

- Patients participating in an interventional clinical study within 30 days before start of 1L

All sites are asked to document all of their patients with the fulfilled inclusion and not fulfilled exclusion criteria, starting with the earliest start (in part 1) and the longest follow-up period (in part 2), respectively. The patients should be treated with the systemic 1L therapy in the site and data should be available in the medical records of the sites. The enrollment will be competitively over all participating sites without a limitation for the single sites. In part 2 quotas for groups with ICI + TKI and ICI + ICI and with the specific therapy avelumab + axitinib or nivolumab + ipilimumab will be set up.

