- Progression-free survival (PFS) for 1L therapies, expressed as median and as rates at timepoints of 6, 9, 12 and 18 months after start of 1L

Secondary Objectives:

- Overall survival (OS) of 1L therapies, expressed as median and rates at timepoints of 12 and 18 months after start of 1L therapy
- Best response in 1L overall and in dependence of administered drug regimen
- Progression-free survival of 1L therapies in dependence of specific drug regimen
- Pre- and post-treatments (i.e. surgery, radiotherapy, medicinal therapies) before/after TKI + ICI and ICI + ICI in 1L
- Duration of response (DoR) in 1L overall and in dependence of administered drug regimen (TKI + ICI or ICI + ICI)
- Frequency of dose modifications and temporary/permanent discontinuations of 1L therapies and their reasons
- Proportions of modifications by dose reduction compared to cancelling single applications
- Effectiveness (PFS, OS and best response) of administered 1L therapies under real world conditions by medical specialty (urology, medical oncology) and setting (practice, hospital)

Study Design	This is a retrospective, non-interventional, observational, multicenter, Medical Chart Review project in patients with aRCC, who received a systemic 1L therapy between 01 January 2020 – 31 December 2021 under daily routine conditions in hospitals or practices in Germany. At timepoint of enrollment of patients, all decisions for specific treatment regimen or investigations were already made under discretion of the physicians and in accordance to the routine clinical practice. The study should describe and analyze in part 1 and part 2 for the the treatment situation from adult patients with aRCC in 1L as well as the clinical
---------------------	--

	
outcomes and handling of intolerabilities from combination therapies in 1L under daily routine in general and in relation to specific therapies.
 
Only data from medical records for running therapies between 01 January 2020 - 31 December 2021 will be captured under conditions of full anonymization. Based on the full anonymization a written informed consent by the patients or an advice by participating doctors an Independent Ethical Committee (IEC) regarding accordance with professional law should not be necessary.

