9. RESEARCH METHODS

The present 1L treatment of patients with aRCC in Germany is wide-ranging with several options like combinations of ICI + TKI, ICI + ICI or monotherapies with TKI alone. Some of these therapies are only recommended in specific risk situations or in cases of ineligibilities for ICI, but at present there is only limited information available about decisions in 1L aRCC. Additionally, a higher proportion of patients with combined therapies of ICI + TKI or ICI + ICI show intolerabilities with the necessary for dose modifications or interim / permanent discontinuations of one or both drugs, but the processes of decision finding between dose modifications, interruptions and discontinuation are also unclear, although these processes would be very important for the outcomes of the therapy. In contrast to study protocols with clear specifications for handling AEs, in standard daily care the decision processes seem to be in the discretion of every oncologist. But at present, no detailed information about these

processes in standard daily care are available. Such information is also important as these therapies could be administered under in- or out-patient's settings and by urologists or medical oncologists.
Study design

The general design of this data project is a sampling of data about patients with aRCC receiving a 1L therapy, with a start (part 1) or completion (part 2) in 01 January 2020 – 31 December 2021. Data will be documented retrospectively and under full anonymization by investigators or their designees in a specific eCRF. All analyses and reports will be performed under aggregation of data as secondary data reports.

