9.1.1. Inclusion criteria

Patients must meet all of the following inclusion criteria to be eligible for inclusion in the study:

Part 1 and 2:

- Patients aged ≥ 18 years old
- Patients with histologically/cytologically confirmed renal cell carcinoma (ICD-10 C64)
- Full medical information regarding all treatments before, during and after 1L should be available.

Specific inclusion criteria only for Part 1:

- Patients with locally advanced or metastatic disease and a start of any systemic 1L therapy against RCC between 01 January 2020 and 31 December 2021

Specific inclusion criteria only for Part 2:

- Patients with locally advanced or metastatic disease, who were treated with a combination of ICI + TKI or ICI + ICI as 1L therapy against RCC and who had a completion of this therapy between 01 January 2020 - 31 December 2021 with a follow-up period of at least 3 months after completion of the 1L.

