9.6. Data analysis

The data analysis are carried out for all evaluable patients for whom the inclusion criteria are met, first-line therapy with at least 1 application has been documented and no exclusion criteria exist.

Detailed methodology for summary and statistical analyses of data collected in this study will be documented in a statistical analysis plan (SAP), which will be dated, filed and maintained by the sponsor. The SAP may modify the plans outlined in the protocol; any major modifications of primary endpoint definitions or their analyses would be reflected in a protocol amendment.

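### The only exclusion criterion stops at the start of 1L, so patients who enter an interventional study at or after that point are eligible for a routine-care study and would not be flagged

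*Combined protocol and SAP*

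**What the plan says.** Section 9.1.2 gives one exclusion criterion for both parts: "Patients participating in an interventional clinical study within 30 days before start of 1L". The abstract repeats it. The same section continues: "All sites are asked to document all of their patients with the fulfilled inclusion and not fulfilled exclusion criteria".

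Neither part's inclusion criteria address the setting in which 1L was given. Part 1 takes "Patients with locally advanced or metastatic disease and a start of any systemic 1L therapy against RCC between 01 January 2020 and 31 December 2021". Part 2 takes patients "who were treated with a combination of ICI + TKI or ICI + ICI as 1L therapy against RCC", subject to completion and follow-up conditions. The analysis set in section 9.6 requires that the inclusion criteria are met and that "first-line therapy with at least 1 application has been documented and no exclusion criteria exist".

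The intended scope is stated elsewhere. The abstract's study design describes patients treated "under daily routine conditions in hospitals or practices in Germany" and says that decisions on regimen and investigations "were already made under discretion of the physicians and in accordance to the routine clinical practice". Section 9.8 requires the data to arise under standard conditions. Section 10 states that all patients had standard daily care with no added investigations or interventions.

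**The concern.** The criterion works as a washout before 1L. The study's interest lies in what happens during 1L, and the criterion does not cover that period.

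The protocol itself explains why this matters. Section 9 says: "In contrast to study protocols with clear specifications for handling AEs, in standard daily care the decision processes seem to be in the discretion" of the treating oncologist. Section 7 makes the same contrast between trial treatment and standard care, and puts particular emphasis on how intolerabilities of combination therapy are handled. Where a study prescribes dosing, dose modification or imaging, a patient in it contributes protocol-driven data to outcomes meant to describe physicians' own decisions. The outcomes at stake are the frequency and handling of modifications and discontinuations, and the timing of recorded progression in PFS.

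The gap would be hard to close later. Section 9.3 rules out queries because entry is fully anonymised. The rejection rules in sections 9.3, 9.7 and 9.8 concern implausible, inaccurate or missing data, and a well-documented trial patient has none of these faults.

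**Working it through.** **Step 1: which patients the text admits.** The eligibility text can be applied to four cases. Because participation is not defined, two readings are possible: it begins at consent, or it begins with the first study treatment.

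| Case | Begins at consent | Begins at first study treatment |
|---|---|---|
| In an earlier study, still participating in the 30 days before 1L | Excluded | Excluded |
| Consented in the 30 days before 1L; 1L is the study treatment | Excluded | Eligible |
| Entered a study on the first day of 1L | Eligible | Eligible |
| Entered a study after 1L had started | Eligible | Eligible |

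The last two rows are open on either reading. The second row depends on the missing definition.

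**Step 2: whether anything later removes or flags them.** The analysis set in section 9.6 adds only one documented application of 1L. Table 2 in section 9.2 records regimen, doses, modifications and reasons, but not trial participation. An unusual regimen might be noticed; a guideline regimen given within a study would not stand out.

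**Step 3: the planned precision, as a yardstick.** Section 9.4 uses n = z²π(1−π)N / [z²π(1−π) + E²(N−1)] with z = 1.96, π = 0.5, E = 0.05 and N = 10,000.

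- z²π(1−π) = 3.8416 × 0.25 = 0.9604
- n = 9,604 / (0.9604 + 0.0025 × 9,999) = 9,604 / 25.9579 = 369.98, so 370

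The plan's figure reproduces. The yardstick for a PFS rate is a margin of 5 points.

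**Step 4: possible shift in an overall PFS rate.** If a share s of patients has a rate differing by d points from the rest, the overall rate moves by s × d. Neither s nor d is in the documents; both are assumed.

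| Assumed share s | Patients of 400 (Part 1) | Patients of 300 (Part 2) | Shift at d = 5 | Shift at d = 20 |
|---|---|---|---|---|
| 2% | 8 | 6 | 0.1 | 0.4 |
| 5% | 20 | 15 | 0.25 | 1.0 |
| 10% | 40 | 30 | 0.5 | 2.0 |
| 20% | 80 | 60 | 1.0 | 4.0 |

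At d = 20, a shift equal to the 5-point margin would need s = 5/20 = 25%, or 100 of 400 patients.

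**Step 5: subgroup exposure.** Section 9.4 expects 35% of patients in hospitals: 0.35 × 400 = 140. Enrolment is competitive with no site limit (section 9.1.2), so such patients could cluster. If all 8 to 20 were hospital patients, they would form 8/140 = 5.7% to 20/140 = 14.3% of that group. At d = 20 the hospital rate would move by 1.1 to 2.9 points, with no shift in practices. This is a worst-case illustration.

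**The case against.** The strongest reply is that the routine-care restriction already exists. The abstract's study design, section 9.8 and section 10 all say that patients were treated under routine or standard conditions, and section 9.8 words this as a requirement. A site reading section 9.1.2 in that light might leave out a patient on trial-assigned 1L. This shows the intent clearly. It is still not an eligibility rule, and it conflicts with the request that sites document everyone who passes the listed criteria.

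The second reply is that patients in a trial of 1L treatment normally consent before dosing, so the 30-day window catches them. This may hold for many. A reader might infer from the criterion that anyone in a trial during 1L can enter; the documents do not support that, because earlier participation can fall inside the window. What remains certain is entry at or after the start of 1L.

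Third, not every interventional study controls anticancer dosing, imaging or dose modification, and the protocol does not define the term. Bias in PFS is therefore possible, not established.

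Fourth, the obvious remedy of excluding anyone who joins a study at any time during 1L has its own fault. PFS and OS run from the start of 1L. A patient must remain on 1L long enough to join a study, so excluding late joiners selects on an event after the time origin. This objection stands and shapes the fix.

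**Conclusion.** The gap is real and minor. As written, patients whose participation begins at or after the start of 1L are eligible, and no eCRF variable identifies them. That does not match the protocol's own description of its patients. Whether patients who consented before the first dose are also admitted depends on an undefined term.

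A reader might infer that the primary result is materially biased. The documents do not support this: they give no share of trial patients and no difference in outcome. On the assumed 2% to 5% share and 5 to 20 point difference, the overall PFS rate moves by 0.1 to 1.0 points, well inside the 5-point margin. The dose-modification outcomes are more exposed because trial rules act on them directly. The practice and hospital subgroups are more exposed because the same few patients weigh more in a smaller group. Neither effect can be sized from the documents.

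**What to change.** In section 9.1.2 and the abstract, reword the criterion to exclude patients participating in an interventional clinical study within 30 days before or at the start of 1L, including those whose 1L is itself given within such a study. State whether participation begins at consent or at first study treatment.

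Do not exclude patients who join a study after 1L has started. Add a yes/no field with date of entry to the eCRF and Table 2. In the SAP foreseen by section 9.6, specify a sensitivity analysis that censors these patients at study entry or omits them. Keep it secondary to the main analysis: censoring assumes that study entry is unrelated to prognosis, and omission selects on a later event.

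The cost is a few words in two places, one eCRF field with a date, one extra analysis and the loss of a small number of charts. The change should be in place before data collection starts (planned for 1 October 2022), since queries cannot be sent afterwards.

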Study Size	Based on public data the population of patients with aRCC and an indication for a 1L therapy is around $n = 4.500 - 5.000$ patients per year (Robert Koch Institute 2020). In the period of 01 January 2020 – 31 December 2021, which is the main period of interest in the study for completing or starting 1L therapies, the total population of patients with aRCC would be around $n = 9.000 - 10.000$ patients. To estimate the needed number of patients in the study to reach adequate representation across Germany, the following common formula is used $n = \frac{z^2 \pi(1 - \pi)N}{z^2 \pi(1 - \pi) + E^2(N - 1)}$ 
N = population of patients with aRCC and indication for 1L = 10.000 patients in 24 months Π = 0,5 (consensus, if attribute is unknown before study) E = margin of error = 5% = 0,05 Z = 1,96 (for confidence interval of 95%)
 
Based on these assumptions (PFS of 1L therapies included in guidelines was 8.4 – 15.1 months in clinical studies) the number of patients needed for representative statement regarding the primary objective (= PFS rates at defined time points under real world conditions) is at least $n = 370$. With a buffer of around 10% the sample size in the study should be $n = 400$ patients with aRCC and 1L therapies in the period from 01 January 2020 – 31 December 2021. Based on published data for PFS it could be

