7. RATIONALE AND BACKGROUND

In clinical trials, patients are treated strictly according to a study protocol and show sometimes different risk factors, fewer comorbidities or a lower age than patients under standard care conditions. However, there is limited larger data collections on current therapy behavior in the 1L of patients with RCC, who are treated under standard care conditions in Germany.

The special interest of this retrospective Medical Chart Review project is to obtain in a Part 1 more precise data for the distribution of different 1L therapies of patients with aRCC, which have started within 01 January 2020 – 31 December 2021 and are representative for Germany. In Part 2 the effectiveness, sequences as well as the frequencies and handling of intolerabilities of combination therapies (ICI + TKI or ICI + ICI) in 1L aRCC will be analyzed by capturing data of patients, who completed a 1L in 01 January 2020 – 31 December 2021 with a follow up period of at least 3 months after completion. All data describe also the current therapy behavior and the resulting clinical effectiveness of the individual therapy protocols used in the 1L. These data allow the transferability of the results from clinical studies to standard care as well as the specific handling of intolerabilities. Particular emphasis is placed on analyses of this handling of intolerabilities during combination therapies with ICI + TKI or ICI + ICI. Information about current processes in decision findings regarding dose modifications or interruptions or interim / permanent discontinuations of one or both drugs can help to unify processes and to develop standard recommendations for daily care situations. Another point of the data analysis lies in the area of the medical disciplines and institutions that initiate and carry out 1L therapies for aRCC under standard care conditions. Questions about the different therapeutic behavior between urologists and medical oncologists, between practices and hospitals and between different regions in Germany are of particular relevance.

[figure not shown]
In conclusion, the rationale of this study is more clarity in the effectiveness of different 1L therapies, more clarity in the accordance of 1L therapies to national guidelines and more clarity in the handling of intolerabilities or other situations where dose modifications or discontinuation of treatment occurs

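### If a Part 2 quota fills before every eligible chart is entered, taking the longest follow-up first selects survivors, unless follow-up means calendar time

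*Combined protocol and SAP*

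**What the plan says.** The enrolment rule stands in section 9.1.2, below the exclusion criterion. It opens with a request for completeness, "All sites are asked to document all of their patients with the fulfilled inclusion and not fulfilled exclusion criteria", and continues with an order of work, "starting with the earliest start (in part 1) and the longest follow-up period (in part 2), respectively". It then adds: "The enrollment will be competitively over all participating sites without a limitation for the single sites". For Part 2 it announces regimen quotas ("In part 2 quotas for groups with ICI + TKI and ICI + ICI", and for two specific combinations) without giving their sizes.

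Section 9.1.1 limits Part 2 to patients who completed a combination 1L in 2020–2021 "with a follow-up period of at least 3 months after completion of the 1L". Part 1 takes patients with "a start of any systemic 1L therapy against RCC between 01 January 2020 and 31 December 2021". Section 9.4 sets targets of 400 for Part 1 and 300 for Part 2.

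Follow-up period is not defined. Section 9.5 says that the eCRF carries each patient's course to the present date, death or loss to follow-up. No screening log, completeness check or stopping rule at the targets is given, and the limitations in section 9.8 do not mention the order of entry.

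**The concern.** An order of entry is harmless if every eligible chart is entered. Once a target or quota closes, it decides who is left out.

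In Part 2 the sorting variable may itself be an outcome. Among patients who completed 1L at the same time, those who die soon afterwards have the shortest observed follow-up and go to the bottom of the list. Section 7 gives Part 2 the task of describing effectiveness and treatment sequences for the combinations, and section 8.2 lists OS and post-treatments as secondary objectives. Patients who live longer after 1L also have more opportunity to receive later lines. Patients who were never entered leave no data from which the selection could be corrected.

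In Part 1 the sorting variable is the start date. That does not select on outcome, but it could thin out late-2021 starts in a sample meant to give "more precise data for the distribution of different 1L therapies of patients with aRCC" that is representative for Germany.

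**Working it through.** **The plan's own figure.** Section 9.4 uses n = z²π(1−π)N / [z²π(1−π) + E²(N−1)] with z = 1.96, π = 0.5, E = 0.05 and "N = population of patients with aRCC and indication for 1L = 10.000 patients in 24 months". The numerator is 3.8416 × 0.25 × 10,000 = 9,604. The denominator is 0.9604 + 0.0025 × 9,999 = 25.958. The result is 369.98, so 370 reproduces; the target of 400 is 8.1% above it. The formula presumes a random sample and is silent on order of entry.

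**Part 2: assumptions.** Survival after completion is exponential with median m = 12, 18 or 24 months. Completions are spread evenly over the 24-month window. Follow-up is observed time. The documents give no figure for m or for the number of eligible completers.

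*Step 1, true 12-month post-completion survival:* 2^(−12/m) = 50%, 63%, 71%.

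*Step 2, effect of the 3-month minimum if early deaths are dropped:* 2^(−12/m) / 2^(−3/m) = 2^(−9/m) = 0.595, 0.707, 0.771. The rule alone adds about 9, 8 and 6 points.

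*Step 3, effect of longest-first.* If data are cut at least 12 months after the last completion, everyone with less than 12 months of follow-up has died (loss to follow-up aside). Deaths between months 3 and 12 are 40.5%, 29.3% and 22.9% of eligible patients. Leaving out the shortest 10% or 20% therefore removes only deaths, and survival in the remainder is the Step 2 value divided by 0.9 or 0.8.

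| Median after 1L (assumed) | True | All eligible (≥3 months observed) | Longest 90% | Longest 80% |
|---|---|---|---|---|
| 12 months | 50% | 59% | 66% | 74% |
| 18 months | 63% | 71% | 79% | 88% |
| 24 months | 71% | 77% | 86% | 96% |

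With 300 places, the last two columns correspond to 300/0.9 = 333 and 300/0.8 = 375 eligible completers. A simulation with abstraction spread over October 2022 to January 2023 (months 33 to 37 from the start of the window) gives the same values, except 95% in the bottom right cell, because a few late completers are censored before month 12.

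*Step 4, ordering by completion date.* In the same simulation, taking the earliest-completed 80% of eligible patients leaves 59%, 71% and 77% unchanged. If the 3-month condition no longer removes early deaths, it returns 50%, 63% and 71%.

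**Part 1.** The site figures in section 9.4 give 15×8 + 15×8 + 10×16 = 400 to 15×12 + 15×12 + 10×24 = 600 eligible starts, before exclusions and rejected files. Against 400, the surplus is 0 to 200 patients (0% to 33%). With even starts and all sites working in step, the earliest 400 reach month 24 if supply is 400, month 400/500 × 24 = 19.2 if it is 500, and month 400/600 × 24 = 16 if it is 600.

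**The case against.** The strongest reply is that the sentence already asks for all patients and that no stop at 400 or 300 is written. This stands: the selection is conditional. But competitive enrolment with quotas implies that entry closes at some point, and nothing checks completeness.

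Second, longest follow-up is paired with earliest start and may simply mean the oldest completions. On that reading the ranking adds no survivor selection. This also stands, but the term is undefined and some 40 sites would interpret it. Calendar time would make the 3-month criterion idle: the last eligible completion (31 December 2021) is nine months before data collection opens on 1 October 2022. That points towards observed time without proving it.

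Third, patients who qualify for both parts transfer automatically from Part 1 (abstract, Variables), so Part 2 is not filled purely longest-first. This may soften the effect.

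A reader might infer that Part 2 OS is therefore biased upward. The documents do not support that as a net statement. OS is measured from start of 1L, whereas the figures above run from completion. Part 2 also omits patients still on 1L, which may pull OS down. Nor would entering every chart remove all bias, because the 3-month minimum may already exclude early deaths.

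A reader might also infer that Part 1 stops at month 16 or 19. That needs a supply above 400, a hard stop, and sites moving in step. Where sites work at different speeds, late starts are thinned rather than cut off. Earliest-first also serves the 18-month PFS rate: with collection ending on 30 January 2023, only starts up to about 30 July 2021 can have 18 months of follow-up.

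**Conclusion.** The point holds for Part 2 under two conditions: a quota fills before all eligible charts are entered, and follow-up is taken as observed time. Longest-first then adds about 15 to 18 points to 12-month post-completion survival if 80% of eligible completers are entered, and about 7 to 9 points if 90% are. This comes on top of the 6 to 9 points due to the 3-month minimum if it drops early deaths. The sizes rest on assumed exponential survival and an assumed pool. Under the two conditions, the direction for post-completion survival does not depend on those assumptions. For OS from start of 1L the net direction remains open.

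For Part 1 the concern is secondary: possible under-representation of late-2021 starts, with no selection on outcome and a real gain in follow-up on the other side. The documents give no figure for how regimen use changed over the window, so its effect on the regimen distribution cannot be sized.

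**What to change.** **Part 2, section 9.1.2:** order charts by date of 1L completion, or at random, within each quota group, and never by observed follow-up. Random order also avoids favouring early completers.

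**Part 2, section 9.1.1:** define the 3-month follow-up as potential calendar time from completion to data collection, so that patients who die within 3 months stay eligible.

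**Part 1:** either enter all eligible charts, as section 9.1.2 already asks, and say that enrolment does not stop at 400; or keep the order, report the calendar distribution of starts, and limit the claim to represent 2020–2021 accordingly. Fixed numbers per half-year are not needed.

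The cost is a few lines of text and a dated list of eligible patients at each site. The downside is that some entered Part 2 patients will have short observed follow-up. No sample size changes.
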